BMI. Weight will be measured in duplicate in light clothing on a calibrated scale (Model #PS6600, Belfour, Saukville, WI) to the nearest 0.1 kg. Standing height will be measured in duplicate with a portable stadiometer (Model #IP0955, Invicta Plastics Limited, Leicester, UK). BMI will be calculated as weight (kg)/height (m²). Session attendance for group exercise (RGV only) and support sessions will be obtained from records maintained by the health coach, and expressed as the percent of possible sessions from 0-6 mos. and 7-12 mos. Attendance for adults with AD, enrolled caregivers, and alternative caregivers will be recorded separately. Use of recorded videos (frequency and duration of access, RGV only) will be assessed using Dropbox® analytics. Self-monitoring of physical activity will be assessed as the percentage of days with Fitbit data over a minimum of 8 hrs., between 6 am and midnight (0-6, 7-12, 13-18 mos.). Peer interactions (RGV only). Staff will review video recordings of a random sample of 33% of group exercise sessions to identify and classify both peer to peer, and health coach to participant interactions. Interactions will be quantified and coded as verbal/non-verbal (waving, pointing, shaking head in agreement/disagreement), and as positive, neutral or negative, relative to support, using a modification of a checklist we previously developed for a group video exercise intervention for adolescents with IDD (62). Caregiver support will be assessed using the percentage of group exercise sessions (RGV) and/ or individual support sessions completed by both the person with AD and their caregiver. Quality of the dyadic relationship will be assessed at baseline, 6, 12, and 18 mos. using the dyadic relationship scale (DRS) which measures negative and positive dyadic interactions from the perspective of both the patient and the caregiver. The DRS has acceptable construct, discriminant, and concurrent validity, as well as reliability for both patients and caregivers(105). We will evaluate the impact of the DRS on our primary and secondary outcomes as well as examine changes across time in both groups. Type of dyadic relationship. We will document the type of caregiver, e.g., spouse, adults child, paid staff, and evaluate the impact of caregiver on our primary and secondary outcomes. Number of caregivers. We will document the number of different caregivers for adults with AD and evaluate the impact of the number of caregivers on our primary and secondary outcomes. Level of dementia will be assessed at baseline using the CDR(110) which has shown acceptable validity(111) and reliability(112). Energy Expenditure of Remote Sessions Energy expenditure of the remote sessions will be assessed in a volunteer sample of both patient and caregiver using a previously validated portable, open-circuit indirect calorimeter (Cosmed, Italy) which measures breath-by-breath ventilation, expired oxygen, and carbon dioxide. Study staff will schedule the assessment with participants which will involve an

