Secondary aim: To compare adults with AD and their caregivers randomized to RGV or ECU on the following outcomes across 18 mos. *Adults with AD:* MPA (min/wk.), sedentary time (min/wk.), percentage meeting 150 min/wk. goal, functional fitness, activities of daily living (basic/instrumental), quality of life, residential transitions, neuropsychiatric symptoms, and cognitive function. *Caregivers:* MPA (min/wk.), sedentary time (min/wk.), functional fitness, quality of life, and caregiver burden. Similar mixed models will be fitted separately for these outcome variables to examine group effect, time effect, and group-by-time interaction while controlling for the number of contacts with research staff and the baseline characteristics imbalanced between participant subgroups.

Exploratory aim: To evaluate the influence of process variables/participant characteristics on MPA in adults with AD and their caregiver across 18 mos.: age, sex, BMI, attendance (exercise/support sessions), use of recorded sessions, PA self-monitoring, peer interactions during group sessions, caregiver support, type and quality of the dyadic relationship, number of caregivers, and level of dementia. If MPA is not significantly different between RGV and EUC across 18 mos., i.e., no significant group effect or group-by-time interaction, we will combine the two arms and examine associations of the process variables/characteristics with MPA in mixed modeling. However, if a significant between-arm difference in MPA is identified, we will determine whether the process variables/characteristics enhance or attenuate the treatment effects, i.e., moderation, by testing a 2-way interaction with the group effect and/or a 3-way interaction with the group-by-time interaction term. In addition, we will examine how caregiver MPA influences the MPA of adults with AD over the 6-mo. active intervention, 6 mos. maintenance, and 6 mos. no contact. Some variables will be measured only at baseline, some will be summarized across the trial, while others will be assessed at specific time points. Thus, we will carefully design our models to assure the appropriateness of the analysis.

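### Exploratory aim: arm-interaction tests cannot be estimated for the RGV-only process variables, and cannot be read as moderation for process variables that arise after randomisation

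*Combined protocol and SAP*

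**What the plan says.** Section V.A, Exploratory aim, puts two kinds of variable in one list. Some are participant or dyad characteristics: age, sex, BMI, type and quality of the dyadic relationship, number of caregivers and level of dementia. Others describe engagement with the programme: "attendance (exercise/support sessions), use of recorded sessions, PA self-monitoring, peer interactions during group sessions, caregiver support".

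The analysis then branches on the 18-month MPA result. With no significant group effect or group-by-time interaction, the arms are combined and associations with MPA are examined. With a significant difference, "we will determine whether the process variables/characteristics enhance or attenuate the treatment effects, i.e., moderation", and the method is "testing a 2-way interaction with the group effect and/or a 3-way interaction with the group-by-time interaction term". Neither branch separates any subset of the list.

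The Exploratory outcomes part of the assessment section says where each variable exists:

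- Attendance: "Session attendance for group exercise (RGV only) and support sessions will be obtained from records maintained by the health coach".
- Recordings: "Use of recorded videos (frequency and duration of access, RGV only) will be assessed using Dropbox® analytics".
- Peer interactions: the entry opens "Peer interactions (RGV only" and is coded from videos of group sessions.
- Caregiver support: "Caregiver support will be assessed using the percentage of group exercise sessions (RGV) and/ or individual support sessions", counting those completed by both members of the dyad.
- Self-monitoring: percentage of days with enough Fitbit data, summarised over months 0-6, 7-12 and 13-18, in both arms.

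The Exploratory aim closes by noting that the variables are measured at different times and by promising careful model design. It names no method.

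**The concern.** A moderation test asks whether the RGV-minus-EUC difference in MPA changes with the level of a third variable. That requires the variable to have values in both arms, and its value must not itself be a result of assignment.

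Three of the measures fail the first requirement because EUC has no group sessions, session recordings or group peers. Three others exist in both arms but accrue during the intervention, so they may fail the second. One route is explicit in the plan: under Self-monitoring, RGV dyads also receive Fitbit reminders during group exercise sessions, which EUC dyads do not attend.

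At stake is what the exploratory aim can conclude. Some planned models would not run as specified. Others would run and could report adherence to the programme as evidence about who benefits from it.

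**Working it through.** The plan gives no figure to reproduce on this point. The checks are algebraic, with one illustration.

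**1. How much of the list is affected.** Counting type and quality of relationship separately, the list has 12 items: age, sex, BMI, attendance, recordings, self-monitoring, peer interactions, caregiver support, relationship type, relationship quality, number of caregivers and dementia level. Five are post-randomisation process measures: attendance, recordings, self-monitoring, peer interactions and caregiver support. Attendance is one item with two parts, and only the exercise part is RGV-only. Splitting it gives 6 of 13: three RGV-only and three shared.

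**2. Estimability for RGV-only variables.** Let G = 1 for RGV and 0 for EUC, t = time, X = process variable.

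- Two-way model: 1, G, t, Gt, X, GX (6 columns).
- Three-way model: adds Xt and GXt (8 columns).

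If X equals a constant c throughout EUC, then X = GX + c(1 − G), so

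- X − GX = c·1 − c·G
- Xt − GXt = c·t − c·Gt

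Each identity removes one dimension. With c = 0, GX is simply X. The rank of the fixed-effects design was checked numerically with 50 dyads per arm (100 dyads, 1:1) and the five MPA visits (0, 3, 6, 12, 18 months):

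| X | Two-way rank | Three-way rank |
|---|---|---|
| Observed in both arms | 6 of 6 | 8 of 8 |
| RGV only, EUC = 0 or a constant | 5 of 6 | 6 of 8 |
| RGV only, EUC missing (RGV rows only) | 3 of 6 | 4 of 8 |

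In the second row the interactions are aliased with lower-order terms. In the third, G is constant and the arm effect goes too. Neither result depends on sample size. The multiple imputation in Section V.A, Missing data, is for nonresponse and cannot supply values for sessions that EUC does not have.

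**3. Combined-arm branch.** If EUC is coded zero and arm is left out, the pooled slope of MPA on X is (W·b + B·d/m)/(W + B). Here b is the slope within RGV, d the arm difference in mean MPA, m the RGV mean of X, and W and B the within-RGV and between-arm sums of squares of X. The slope therefore mixes the association of interest with the arm contrast.

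**4. Shared post-randomisation variables.** The interaction is estimable, so the issue is its meaning. An illustration used 100 participants, 2,000 replicates, a constant true arm effect of 10 with SD 30 (so no moderation), and a latent trait of variance 1 that affects the outcome (loading 15) and X (loading a, residual SD 0.7). The trait structure and loadings are assumptions, not figures from the plan.

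The expected slope of outcome on X in an arm is 15a/(a² + 0.49).

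- a = 0.7 gives 10.5/0.98 = 10.71.
- a = 0.1 gives 1.5/0.50 = 3.00.
- Expected spurious interaction with 0.7 in RGV and 0.1 in EUC: 10.71 − 3.00 = 7.71 (simulated 7.57).

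Rejection rates of the 5% interaction test:

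- X unrelated to the trait: 4.7%.
- Equal loadings (0.7 in both arms): 5.7%.
- Loadings 0.7 and 0.1: 18.2%.

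If RGV also raises X by 0.5 with equal loadings, rejection stays at 5.9%, but the arm coefficient becomes 10 − 10.71 × 0.5 = 4.64 (simulated 4.50), although the true effect is 10.

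**5. Caregiver support.** RGV has three group sessions a week in months 0-6; both arms have two support sessions a month. Taking six months as 26 weeks:

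- RGV: 3 × 26 = 78 group sessions plus 2 × 6 = 12 support sessions, total 90.
- EUC: 12 support sessions.

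If the two types are pooled, 78/90 = 87% of the RGV denominator is a session type EUC never has. If only support sessions are used, the share is 0%. The wording allows either.

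**The case against.** Several points on the other side have force.

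- **The plan recognises that the variables differ in timing.** A reader might infer that post-randomisation variables are being treated as baseline moderators. The text does not say that: it distinguishes variables measured at baseline, summarised over the trial, or assessed at set times. What remains is that the promise of careful modelling is about timing, names no method, and leaves the stated interaction test applying to all of them.
- **A reader might infer that caregiver support is fixed on different sessions in each arm.** The and/or wording does not fix it. Support sessions run in both arms, so a common measure is permitted, though not required.
- **A reader might infer that attendance cannot be tested at all.** Only its exercise part is RGV-only; support-session attendance exists in both arms.
- **Rank deficiency is partly self-correcting.** With arm in the model, dropping the redundant columns leaves an X coefficient that is the slope within RGV, and an inestimable term cannot itself yield a false moderation finding. That stands, but the coefficient is then a non-randomised association, not the moderation the plan announces.
- **The 18% figure rests on assumed loadings.** That also stands. With equal loadings the rate is near nominal, so the figure shows a mechanism and not an expected error rate for this trial.
- **The aim is exploratory, and the moderation tests run only after a significant arm difference.** Correct, and it limits the consequence.

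**Conclusion.** The concern holds in two parts of different strength.

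For recorded-video use, peer interactions and the group-exercise part of attendance, the arm and arm-by-time interactions cannot be estimated. This follows from the plan's own RGV-only labels and needs no further assumption.

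For support-session attendance, Fitbit self-monitoring and caregiver support, the interaction can be fitted but cannot be read as moderation of the treatment effect. This rests on the variables arising after randomisation and possibly being affected by arm. The size of any distortion cannot be derived from the documents. Caregiver support has the added ambiguity that it may draw on different sessions in each arm.

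Five of 12 listed items are touched. Age, sex, dementia level and relationship type are unaffected, as are BMI and relationship quality if their baseline values are used. A reader might also infer that the trial's main result is compromised; it is not, because the primary and secondary comparisons do not use these models. The stated rule is nevertheless wrong as written, and the correction is cheap.

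**What to change.** Amend Section V.A, Exploratory aim, as follows.

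1. Limit arm-interaction moderation tests to baseline values of variables measured in both arms: age, sex, baseline BMI, CDR level, relationship type, baseline dyadic relationship scale score, and number of caregivers at baseline. The baseline value must be named for BMI and the relationship scale because both are also measured later. It must be named for number of caregivers because Exploratory outcomes gives no time point, although Baseline equivalence lists it among the variables inspected at baseline.
2. Analyse group-exercise attendance, recorded-video use and peer interactions within RGV, labelled as non-randomised associations with MPA. In the combined-arm branch, do not pool them with EUC coded as zero.
3. Report support-session attendance, self-monitoring and caregiver support as within-arm associations or as mediators, stating that confounding by general adherence is possible in either case.
4. Whenever arms are compared, compute caregiver support on individual support sessions in both.

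No new data are needed. The cost is SAP wording and fewer moderation tests. The analyses under items 2 and 3 remain observational and should be reported as such.

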We will study older adults (age ≥ 55 yrs.) with mild to moderate AD (n=100) and their caregiver (n=100) randomized (1:1) to one of two intervention delivery strategies for increasing MPA; real-time group video conferencing (RGV) vs. enhanced usual care (EUC). All participants will be provided with an iPad® for intervention delivery, Fitbit for self-monitoring MPA, and will be asked to complete 150 min of MPA/wk. Dyads in the RGV arm will be asked to complete three 45 min sessions that include aerobic, resistance, and balance/coordination exercises delivered by a trained

health coach via Zoom® software on an iPad® during mos. 0-6, and 1 session/wk. during mos. 7-12 to groups of 5-8 dyads in their home. Dyads in the EUC arm, will be given an exercise plan to do own their own. Dyads in both arms will be provided with written materials regarding exercise and physical activity from the National Institute on Aging and will be asked to complete brief (15-20 min) FaceTime™ meetings (0-6 mos.= 2/mo.; 7-12 mos.= 1/mo.) with the health coach to discuss progress, provide support and receive additional guidance on how to increase MPA. Our primary outcome, MPA, will be assessed by accelerometer across the 6 mo. active intervention and total 18 mo. study (secondary outcome).

C. Sample size, statistical methods, and power calculation

We will recruit 100 adults with AD and their caregiver (100 dyads) at baseline to achieve adequate power to test both short-term (0-6 mos.) and long-term (0-18 mos.) effects of the intervention. Our power calculation, based on 21 measurements of MPA, 35 measurements of secondary and exploratory outcomes, a previously observed correlation of 0.22 between repeated measures, and a high attrition rate of ~20%, indicated that this sample size (≥ 42 /arm after attrition) would produce $\geq 80\%$ power to detect an anticipated difference of 10-min/d in MPA ($SD=30$ min/d; $f=0.17$) between adults with AD randomized to RGV and EUC during the active intervention (0-6 mos.). This sample size would also yield $\geq 81\%$ power to test a between-arm difference as small as $f=0.15$, e.g., 6 ± 30 min/d in MPA, during maintenance (7-12 mos.) and no contact (13-18 mos.).

D. Subject Criteria (See Vulnerable Populations appendix, if applicable):

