Statistical design. Baseline equivalence. The distributional properties of baseline demographic characteristics (MPA, BMI, age, sex, race/ethnicity, etc.) and dyadic relationship between adults with AD and their caregiver (quality, type, number of caregivers) will be inspected within the sample and between the RGV and EUC arms. Variables that demonstrate a significant nonequivalence between RGV and EUC arms will be statistically controlled in the hypothesis testing to improve accuracy of our inferences on intervention effects. Additionally, variables that significantly differ between dyads that dropped out and those that did not will be controlled to minimize any systematic bias stemming from attrition.

Primary aim: *To compare MPA (min/wk.) across the 6-mo. active intervention in adults with AD randomized to RGV and EUC.* Our analysis will account for/evaluate the clustering of observations (repeated measurements; level 1) within participants (level 2) and dyads (level 3; if multiple caregivers) by estimating intra-class correlations and variances/covariances of regression

coefficients at, and across, different levels in random-effects multilevel models (mixed models). To address the aim, models will examine overall between-arm difference in MPV across time (group effect), linear/non-linear change in MPV over time (time effect), and, if appropriate, between-arm difference in this change (group-by-time interaction), while controlling for (i) the number of contacts with research staff and (ii) the baseline characteristics imbalances between participant subgroups (RGV vs. EUC, dropouts vs. completers). For example, a significant interaction would indicate that adults with AD in the RGV arm achieve more minutes of MPA compared to those in the EUC arm and this difference becomes greater as intervention participation increases, i.e., in the later mos.

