Missing data. Missing data is anticipated due to either attrition, e.g., participant dropout, or nonresponse, e.g., ActiGraph non-wear or malfunction. Our intent-to-treat approach will employ full information maximum likelihood (FIML) estimation in the modeling, which does not discard participants who dropped out but utilizes all available data from their partial measurements, thereby producing unbiased parameter estimates and smallest possible standard errors. Missing observations due to nonresponse will be handled by Monte Carlo Markov Chain (MCMC) multiple imputation (MI) (114). A sufficient number of imputed datasets will be created to ensure accurate recovery of missing data and analysis results from each imputed dataset will be combined to make valid statistical inferences. Our imputation process will incorporate a number of auxiliary variables, thereby satisfying the missing at random (MAR) assumption (115). The state-of-the-science on missing data indicates that FIML and MI are extremely robust and leads to unbiased generalizability (116).

V. Bibliography / References / Literature Cited

1. Alzheimer's Association. Alzheimer's Disease Facts and Figures: Alzheimer's & Dementia 2017. 2017.

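### Full maximum likelihood with no small-sample correction makes the between-arm test on continuous outcomes slightly liberal (about 5.4–6.1% at a nominal 5%): a minor correction

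*Combined protocol and SAP*

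**What the plan says.** In Statistical and Data Analysis, the paragraphs on the primary and secondary aims specify random-effects multilevel models. They test a group effect, a time effect and, where appropriate, their interaction. The primary-aim model is to control for "i) the number of contacts with research staff and (ii) the baseline characteristics imbalances between participant subgroups". The Baseline equivalence paragraph makes the second part data-dependent: a variable enters if it differs significantly between arms, or between dyads that drop out and those that stay.

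The Missing data paragraph names the estimator: "Our intent-to-treat approach will employ full information maximum likelihood (FIML) estimation in the modeling". The reason given is that this is a method "which does not discard participants who dropped out but utilizes all available data from their partial measurements", and the benefit claimed is "thereby producing unbiased parameter estimates and smallest possible standard errors". Item non-response is handled separately by multiple imputation.

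The sample size section gives the numbers: "We will recruit 100 adults with AD and their caregiver (100 dyads) at baseline", with at least 42 per arm left after attrition.

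The plan does not mention REML, a denominator degrees-of-freedom method, a reference distribution for the tests, or a significance level.

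**The concern.** ML variance components take no account of the degrees of freedom spent on fixed effects, so they are biased downward. The main effect of arm is estimated between persons, so the number that matters is the number of adults (84 to 100), not the number of daily accelerometer records. The more person-level covariates the model carries, the larger the bias, and here the data decide how many there are.

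The consequence has one direction: intervals for the RGV–EUC difference are slightly too narrow and p-values slightly too small. The primary-aim paragraph also plans to estimate intra-class correlations and variance components, and these inherit the bias. The stated reason for FIML does not require ML, because REML also uses all partial data.

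**Working it through.** **Inputs.** From the sample size section: 100 adults enrolled 1:1, at least 84 after attrition, 21 MPA measurements, correlation 0.22, SD 30 min/d, f = 0.17, attrition about 20%. Assumed: two-sided 5%, and a random-intercept structure. The reference distribution is not stated, so normal and t are both shown.

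**The plan's own figure.** The plan gives no error rate, but its power statement confirms the inputs. For a repeated-measures between-groups test, the noncentrality is f²·N·m/(1+(m−1)ρ) = 0.17² × 84 × 21 / (1 + 20 × 0.22) = 50.98/5.4 = 9.44. On F(1, 82) this gives 85.9% power, so the stated bound of at least 80% is met.

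**How many fixed effects.** The intercept, arm and number of staff contacts give k = 3 as the minimum. The Baseline equivalence paragraph names eight candidates: MPA, BMI, age, sex, race/ethnicity, and relationship quality, type and number of caregivers. Suppose each is screened twice at 5%, independently and with no real differences. The expected number of positive screens is 16 × 0.05 = 0.8. Each variable then has a 1 − 0.95² = 9.75% chance of entering, so P(3 or more enter) is about 3.6% and P(5 or more) about 0.04%. Real predictors of dropout, or multi-category variables, would raise this. On this basis k of about 3–5 is the likely range, and k = 8 is already high.

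**Closed form (balanced data).** The ratio of the ML to the unbiased standard error is r = √((n−k)/n). The type I error is P(|t(n−k)| > c·r), with c = 1.96 (normal) or the 97.5% point of t(n−k).

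Example, n = 84, k = 3: r = √(81/84) = 0.982, c·r = 1.96 × 0.982 = 1.925, and P(|t(81)| > 1.925) = 5.8%.

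| n | k | SE too small by | ML, normal | ML, t | REML, normal |
|---|---|---|---|---|---|
| 84 | 3 | 1.8% | 5.8% | 5.4% | 5.3% |
| 84 | 5 | 3.0% | 6.1% | 5.7% | 5.4% |
| 84 | 8 | 4.9% | 6.6% | 6.2% | 5.4% |
| 100 | 3 | 1.5% | 5.7% | 5.4% | 5.3% |
| 100 | 5 | 2.5% | 5.9% | 5.6% | 5.3% |
| 100 | 8 | 4.1% | 6.3% | 6.0% | 5.3% |

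REML with t gives 5.0% by construction.

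**What is due to ML itself.** Unrounded, at n = 84 and k = 3, ML with a normal reference gives 5.78% and REML with a normal reference 5.34%. ML therefore adds 0.44 points, and the normal reference accounts for the other 0.34. At k = 5 ML adds 6.10 − 5.35 = 0.75 points (n = 84) or 5.91 − 5.29 = 0.62 points (n = 100).

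**Check with dropout.** Simulation used 10,000 null trials per setting: random intercept, intra-class correlation 0.22, SD 30, three 7-day visits, 20% monotone dropout. The Monte Carlo standard error is √(0.05 × 0.95/10,000) = 0.2 points.

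| n | Person-level covariates (k) | ML/REML SE | ML variance/true | ML, normal | ML, t | REML, t |
|---|---|---|---|---|---|---|
| 84 | 3 (5) | 0.970 | 0.93 | 6.1% | 5.6% | 4.9% |
| 84 | 6 (8) | 0.951 | 0.89 | 6.6% | 6.2% | 5.0% |
| 100 | 3 (5) | 0.974 | 0.94 | 5.9% | 5.6% | 5.0% |
| 100 | 6 (8) | 0.959 | 0.90 | 6.2% | 5.9% | 4.8% |

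This agrees with the closed form. Random slopes and the combination with multiple imputation were not modelled.

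**The case against.** The strongest reply is that this is a routine software choice at about 100 participants and that its effect is small. That stands. Because FIML keeps dropouts, n is nearer 100 than 84, so the lower figures are the more relevant ones. Adults with no data after baseline could still reduce the effective number.

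A reader might infer an error rate of 7% or more. The formula does give 7.0% at k = 10 and 7.6% at k = 13 (n = 84, normal reference). But those values need nearly all the named covariates to be selected, while the plan admits only variables that differ significantly. They also rest on a normal reference that the plan never specifies.

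A reader might also infer that every secondary analysis is affected to the same degree. The documents do not support that. The percentage meeting the 150 min/wk. goal and residential transitions are binary or event outcomes, to which the (n−k)/n result and REML with Kenward-Roger do not carry over. With a random intercept, the group-by-time interaction is a within-person contrast with far more residual degrees of freedom, so it is much less affected.

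Finally, the phrase "thereby producing unbiased parameter estimates and smallest possible standard errors" might be read as a claim that ML beats REML. In its place under Missing data it can fairly be read as efficiency relative to discarding dropouts. What remains is that the plan names full ML as the estimator and provides no correction.

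**Conclusion.** The point holds as a minor correction. For the between-arm effect on continuous outcomes in 84 to 100 adults with AD, ML makes standard errors about 1.5–3% too small at k of about 3–5, and a nominal 5% test runs at about 5.4–6.1%. At k = 8 the rate is about 6–6.6%. The direction follows from the estimator the plan names.

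The size depends on assumptions: a two-sided 5% level, a random-intercept structure, the number of covariates selected, and the reference distribution. Roughly 0.3 points of the excess under a normal reference would remain with REML and the same reference. The choice to keep dropouts' partial data under missing at random is sound and is not in question.

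**What to change.** For the continuous-outcome models under the primary and secondary aims, state that estimation is by REML, with Kenward-Roger or Satterthwaite degrees of freedom for fixed-effect tests and confidence intervals. Pool over imputed datasets with Barnard-Rubin small-sample degrees of freedom. State the significance level and sidedness. Keep ML for likelihood-ratio comparison of models with different fixed effects, and for the non-Gaussian outcomes (percentage meeting the 150 min/wk. goal, residential transitions). It would help to reword the standard-error phrase so that it plainly means efficiency relative to dropping incomplete cases.

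The cost is a few lines of SAP wording and one estimation option in standard software. At k of 3–5, removing the ML bias widens intervals by a factor 1/r, that is 1.5–3.1%. Moving from a normal to a t reference as well brings the total to about 3–5%. The handling of dropouts and the missing-at-random assumption do not change.
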